**Comments:**

- Titration should be performed first for the basal insulin. For elevated fasting pre-breakfast glucose levels, adjust only the basal insulin dose.
- Once basal insulin level has been titrated to optimum, then mealtime insulin should be titrated.
- Post-prandial glucose levels are estimated 2 hours after the start of the respective food intake.
- Apart from glucose levels, the dose of mealtime insulin should be guided by expected carbohydrate content of the next meal, and expected level of physical activity within next 4-6 hours. If meal is skipped, the dose should be skipped.
- The target should be the lower limit of the range mentioned above, so that the final value will remain in the expected range.

**Appendix III - 4-Point and/or 8-Point Glucose Estimation Time Points**

Time of the day	Specific point (8-point)	Specific point (4-point)
Fasting Before breakfast	1	1
2 hours after breakfast	2	
Before lunch	3	2
2 hours after lunch	4	
Before dinner	5	3
2 hours after dinner	6	
Just before sleep	7	4
At 3±1 AM	8	

**Comments:**

- Specific days on which the SMBG need to be estimated is as mentioned in the **Assessment Schedule**.
- On all days in which SMBG is not mandated by protocol, patients will be advised to self-monitor blood glucose 4 times a day as per standard of care in type 1 diabetes.
- The 8th point time can be adapted for patients on night shift (in discussion with the Investigator) to approximately 4 hours after going to bed.

#### **Appendix IV - Sample Patient Diary Information**

- Trial, site and patient identification information
- Results of 8-point SMBGs performed as per protocol
- Insulin dose information on days where 8-point SMBGs are performed
- Details of hypoglycemic events
- Details of untoward experiences (AEs)
- Details of problems with the disposable pens or needles

**Appendix V - Letter of Approval of Pen Use by the Investigator (for US Sites only)**

***Prohibition of Promotion and Other Practices***

According to the 21 CFR 812.7, an Investigator or any person acting for or on behalf of a sponsor or Investigator shall not:

- Promote or test market an investigational device, until after FDA has approved the device for commercial distribution.
- Commercialize an investigational device by charging the patients or investigators for a device a price larger than that necessary to recover costs of manufacture, research, development, and handling.
- Unduly prolong an investigation. If data developed by the investigation indicate in the case of a class III device that premarket approval cannot be justified or in the case of a class II device that it will not comply with an applicable performance standard or an amendment to that standard, the sponsor shall promptly terminate the investigation.
- Represent that an investigational device is safe or effective for the purposes for which it is being investigated.

The format below should be followed for the letter of approval.

The protocol identification code for the study in the IND	
Name and address of the Investigator	
The name and address of the sub-Investigators who will be assisting the Investigator in the conduct of the study	
The name and address of the medical school, hospital or other research facility where the clinical investigations will be conducted	
The name and address of the clinical laboratory facilities to be used in the study	
The name and address of the institutional review board that is responsible for review and approval of the study	

AE(s)	Adverse Event(s)
ALT	Alanine Transaminase
ANCOVA	Analysis Of Covariance
AST	Aspartate Transaminase
BMI	Body Mass Index
CI	Confidence Interval
CMH	Cochran-Mantel-Haenszel
CRF	Case Report Form
DCCT	Diabetes Control And Complications Trial
DNA	Deoxyribonucleic Acid
ECG	Electrocardiogram
eCRF	Electronic Case Report Form
EOT	End Of Treatment
FDA	Food and Drug Administration (United States)
FPG	Fasting Plasma Glucose
HbA1c	Glycosylated Hemoglobin
HBsAg	Hepatitis B Surface Antigen
HCP	Host Cell Protein
HIV	Human Immunodeficiency Virus
ITT	Intention To Treat
IU	International Unit
IVRS	Interactive Voice Response System
IWRS	Interactive Web Response System
LDL	Low Density Lipoprotein
LS	LSmeans
MedDRA	Medical Dictionary for Regulatory Activities
MI	Multiple Imputation
MMRM	Mixed Model for Repeated Measures
mITT	Modified Intent-To-Treat
NAb	Neutralizing Antibody
PP	Per Protocol
SAE(s)	Serious Adverse Event(s)
SD	Standard Deviation

Document:	\\JEEDC-NAS01A\Biosdata\Mylan\INSULIN_GLARGINE\UXA25824\Biostatistics\Documentation\SAP		
Author:	[name] and [name]	Version Number:	Final V1.0
		Version Date:	[27JUL2016]

Template No: CS_TP_BS016 – Revision 3
 Effective Date: 01May2012

Reference: CS_WI_BS005

SMBG	Self-Monitored Blood Glucose
TEAE	Treatment Emergent Adverse Event
T1DM	Type 1 Diabetes Mellitus
T2DM	Type 2 Diabetes Mellitus
WHO	World Health Organization

Document:	\\JEEDC-NAS01A\Biosdata\Mylan\INSULIN_GLARGINE\UXA25824\Biostatistics\Documentation\SAP	Version Number:	Final V1.0
Author:	[name] and [name]	Version Date:	[27JUL2016]

Template No: CS_TP_BS016 – Revision 3
Effective Date: 01May2012

Reference: CS_WI_BS005

1. INTRODUCTION

This document describes the rules and conventions to be used in the presentation and analysis of efficacy and safety data for Protocol MYL-1501D-3003. It describes the data to be summarized and analyzed, including the specifics of the statistical analyses to be performed.

This statistical analysis plan (SAP) is based on protocol version V2.0, dated 06-MAY-2016.

2. STUDY OBJECTIVES

2.1. PRIMARY OBJECTIVE

The primary objective is to test whether Mylan's insulin glargine once daily treatment sequence is equivalent to Lantus® once daily treatment sequence (based on change in [glycosylated hemoglobin] HbA1C from baseline at week 36 when administered in combination with mealtime insulin lispro.

2.2. SECONDARY OBJECTIVES

To compare treatment sequence group of Mylan's insulin glargine to Lantus®, at 36 weeks, when administered in combination with mealtime insulin lispro with respect to:

1. Change in basal insulin dose per unit body weight (U/Kg/day).
2. Immunogenicity: incidence and change from baseline in the relative levels of ADA, incidence and change from baseline in the relative levels of anti-HCP antibodies.
3. Rate of hypoglycemic events per 30 days; and occurrence of hypoglycemia
4. Occurrence of local reactions, systemic reactions and other adverse events.
5. Change in fasting plasma glucose from baseline.
6. Change in 8-point (self-monitored blood glucose) SMBG profile from baseline
7. Device related safety assessment.

3. STUDY DESIGN

Patients with an established diagnosis of T1DM per ADA 2014 criteria who were randomized to the Lantus® treatment arm of the MYL-GAI-3001 study, and who have completed the 52-week treatment period on Lantus® will be eligible to be screened for the study MYL-1501D-3003. The purpose of this study is to assess the interchangeability through testing equivalence between two treatment sequences with respect to the primary end point, Mylan's insulin glargine and Lantus®. Eligible patients from MYL-GAI-3001 study who successfully completed 52 weeks on

Document:	\\IEEDC-NAS01A\Biosdata\Mylan\INSULIN_GLARGINE\UXA25824\Biostatistics\Documentation\SAP		
Author:	[name] and [name]	Version Number:	Final V1.0
		Version Date:	[27JUL2016]

Template No: CS_TP_BS016 – Revision 3
Effective Date: 01May2012

Reference: CS_WI_BS005

Copyright © 2012 Quintiles Transnational Corp. All rights reserved.

The contents of this document are confidential and proprietary to Quintiles Transnational Corp. Unauthorized use, disclosure or reproduction is strictly prohibited.

Lantus® will be randomized 1:1 to one of the treatment sequences. Treatment sequence arm 1 - Mylan's insulin glargine for 12 weeks in period 1 then switched to Lantus® for next 12 weeks in period 2 and additional switch to Mylan's insulin glargine for additional 12 weeks to complete the third treatment period. Treatment sequence arm 2 - Lantus® for 12 weeks in period 1, continue to receive Lantus® in period 2 for 12 weeks and in period 3 for another 12 weeks.

Twelve weeks exposure in each period is considered adequate to assess the efficacy with respect to HbA1c, as well as to compare the safety between the treatment sequence groups. If switching from Lantus® to Mylan's insulin glargine or from Mylan's insulin glargine to Lantus® have an impact on the efficacy or the safety, a discernible difference in efficacy or safety parameters is expected versus the group of patients who are continuing on Lantus® throughout.

After 36 weeks of treatment, patients will resume their baseline treatment with prescribed medications and will have a safety follow up visit after 4 weeks resulting in a total study duration of 40 weeks.

3.1. GENERAL DESCRIPTION

Study Duration:

The maximum possible duration of patient participation in the extension trial is 40 weeks, which includes:

- Treatment period 1: 12 weeks (Week 0 to Week 12).
- Treatment period 2: 12 weeks (Week 12 to Week 24).
- Treatment period 3: 12 weeks (Week 24 to Week 36).
- Follow-up period: 4 weeks follow-up visit (Week 36 to Week 40)

Number of Patients:

Approximately 138 patients with type 1 diabetes who completed the 3001 study on the Lantus will participate in this trial. Approximately 69 patients will be randomized to one of two sequence groups (Treatment sequence arm 1: Mylan's insulin glargine switch to Lantus® sequence group and switch back to Mylan's insulin glargine, or Treatment sequence arm 2: Lantus® to Lantus® to Lantus® sequence group) in a 1:1 ratio. No replacement of patients will be performed if a patient discontinued prematurely from the study. For the modified intent-to-treat (mITT) population, power to demonstrate equivalence with $\pm 0.4\%$ limits will be 90% with 10% patients who don't have at least one baseline and one last period HbA1c data. The power is calculated assuming no true mean group difference and a 0.61% standard deviation. This standard deviation is based on published results for clinical studies with Lantus®.

Allocation to Treatment

Patients who completed the 3001 study on Lantus® will be randomized 1:1 to receive either Mylan's insulin glargine or Lantus® using an IVRS/IWRS. Change of dosing from morning to bedtime or vice versa will not be permitted. If a patient discontinues, the patient will not be allowed to re-enter the extension study.

Blinding

This is an open-label study. To minimize bias, treatment assignments will not be revealed to the central laboratory for the safety (immunogenicity) and efficacy (HbA1c) analyses.

Document:	\\IEEDC-NAS01A\Biosdata\Mylan\INSULIN_GLARGINE\UXA25824\Biostatistics\Documentation\SAP		
Author:	[name] and [name]	Version Number:	Final V1.0
		Version Date:	[27JUL2016]

[figure not shown]
Template No: CS_TP_BS016 – Revision 3
Effective Date: 01May2012

Reference: CS_WI_BS005

Study Treatment

The investigational products used in this trial are Mylan’s insulin glargine (test product) and Lantus® from Sanofi-Aventis (reference product). All patients will receive insulin lispro as mealtime medication. Both investigational products will be provided in a pre-filled disposable pen with a 3 mL cartridge. Mylan’s insulin glargine formulation for injection is a, sterile, clear solution at pH 4. Each mL contains 100 units of insulin glargine (equivalent to 3.64 mg). The excipients of the formulation are identical to those of Lantus®. Humalog (insulin lispro injection, 100 IU/mL), is manufactured by Eli Lilly (administered in Humalog disposable pens).

Table A: Study Flow Chart

3.2. SCHEDULE OF EVENTS

Schedule of events can be found in protocol synopsis (pages 18-19) of the protocol.

Document:	\\JEEDC-NAS01A\Biosdata\Mylan\INSULIN_GLARGINE\UXA25824\Biostatistics\Documentation\SAP		
Author:	[name] and [name]	Version Number:	Final V1.0
		Version Date:	[27JUL2016]

Template No: CS_TP_BS016 – Revision 3
 Effective Date: 01May2012

Reference: CS_WI_BS005

3.3. CHANGES TO ANALYSIS FROM PROTOCOL

- An error was found for primary endpoint in Section 9.2.1 Wording “at 12 week” was deleted.
- The results with MMRM ANCOVA from secondary efficacy analysis will also be used to compare primary analysis results as robustness check. Other sensitivity analyses are added in Section 15.1.4 by using multiple imputation method.

3.4. NOT APPLICABLE SIGNIFICANT CHANGES FROM PREVIOUS AUTHORIZED VERSION

Not Applicable

4. PLANNED ANALYSES

The following analyses will be performed for this study:

Final Analysis

4.1. INTERIM ANALYSIS

Not Applicable.

4.2. FINAL ANALYSIS

All planned analyses identified in this SAP will be performed by Quintiles Biostatistics team following sponsor authorization of this SAP and Database Lock.

5. ANALYSIS SETS

Agreement and authorization of patient included/ excluded from each analysis set will be conducted prior to the final database lock of the study.

All analysis sets described below will be derived at final analysis, based on available data.

Document:	\\JEEDC-NAS01A\Biosdata\Mylan\INSULIN_GLARGINE\UXA25824\Biostatistics\Documentation\SAP	Version Number:	Final V1.0
Author:	[name] and [name]	Version Date:	[27JUL2016]

Template No: CS_TP_BS016 – Revision 3
Effective Date: 01May2012

Reference: CS_WI_BS005

Copyright © 2012 Quintiles Transnational Corp. All rights reserved.

The contents of this document are confidential and proprietary to Quintiles Transnational Corp. Unauthorized use, disclosure or reproduction is strictly prohibited.

5.1. RANDOMIZED POPULATION [RND]

The Randomized (RND) population will contain all patients who are enrolled and randomized to study medication. For analyses and displays based on RND, patients will be classified according to randomized treatment sequence group.

5.2. SAFETY POPULATION

The safety population includes patients who are randomized and take at least one dose of the trial drug. Safety population will be mainly used for safety analyses.

If there is any doubt whether a patient was treated or not, they will be assumed treated for the purposes of analysis.

5.3. INTENT-TO-TREAT POPULATION [ITT]

The ITT population includes all randomized patients (including patients who receive incorrect treatment sequence, do not complete the trial or do not comply with the protocol or used prohibited medication) and have baseline (week 0 visit) and at least one post-baseline visit. The patients under ITT population will be analyzed according to the planned treatment sequence. ITT population will be used for secondary variable analyses.

The sensitivity analysis to check the robustness of primary analysis will be based on the ITT population. All secondary efficacy analyses will be based on the ITT population.

5.4. MODIFIED INTENT-TO-TREAT POPULATION [MITT]

The mITT population includes all randomized patients (including patients who receive incorrect treatment sequence, do not complete the trial or do not comply with the protocol or used prohibited medication) and have at least one baseline (week 0 visit) HbA1c value and one post-baseline HbA1c value at treatment period 3 ($24 < \text{Week} \leq 36$). The mITT will be used for primary analysis.

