5.5. PER PROTOCOL POPULATION [PP]

The PP population includes patients who have at least one baseline and one period 3 value and do not have protocol violations that impact the primary outcome. The patients excluded from the PP population will be identified before database lock (i.e., before unblinding the study team). All protocol deviations and the deviations impacting the primary outcome variable will be documented separately and will be signed off prior to the database lock (i.e., before unblinding the study team). PP population will be used for sensitivity analysis for primary variable.

Document:	\\IEEDC-NAS01A\Biosdata\Mylan\INSULIN_GLARGINE\UXA25824\Biostatistics\Documentation\SAP	Version Number:	Final V1.0
Author:	[name] and [name]	Version Date:	[27JUL2016]

Template No: CS_TP_BS016 – Revision 3
Effective Date: 01May2012

Reference: CS_WI_BS005

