6.3. RETESTS, UNSCHEDULED VISITS AND EARLY TERMINATION DATA

In general, for by-visit summaries, data recorded at the nominal visit will be presented. Unscheduled measurements will not be included in by-visit summaries, but will contribute to the best/ worst case value where required (e.g. shift table).

In the case of a retest (same visit number assigned), the earliest available measurement for that visit will be used for by-visit summaries.

Early termination data will be mapped to the next available visit number for by-visit summaries.

Listings will include scheduled, unscheduled, retest, and early discontinuation data.

Document:	\\JEEDC-NAS01A\Biosdata\Mylan\INSULIN_GLARGINE\UXA25824\Biostatistics\Documentation\SAP	Version Number:	Final V1.0
Author:	[name] and [name]	Version Date:	[27JUL2016]

Template No: CS_TP_BS016 – Revision 3
Effective Date: 01May2012

Reference: CS_WI_BS005

Copyright © 2012 Quintiles Transnational Corp. All rights reserved.

The contents of this document are confidential and proprietary to Quintiles Transnational Corp. Unauthorized use, disclosure or reproduction is strictly prohibited.

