7.3. MISSING DATA

Missing primary and secondary efficacy and safety analysis data will be not imputed except when week 36 HbA1c data is missing due to early discontinuation, exit measurement of that period will be used for endpoint. In addition, for sensitivity analysis of multiple imputation method, if missing values occur in more than 10% of the patients for HbA1C values, then monotone regression for multiple imputations will be used.

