15.1.2. MISSING DATA METHODS FOR PRIMARY EFFICACY VARIABLE

The imputation will not be applied. If week 36 HbA1c is missing then last non-missing values from period 3 will be used.

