15.1.3. PRIMARY ANALYSIS OF PRIMARY EFFICACY VARIABLE

The primary objective of this study is to test the equivalence of changes in HbA1C between two treatment sequence groups at week 36.

The primary efficacy analysis will be performed for the mITT population.

ANCOVA will be performed on the primary outcome variable and the model will include region and sequence group as fixed effect and baseline value (52 weeks in MYL-GAI-3001) as covariate using mITT population. A 95% confidence interval for the difference between two treatment sequence groups for mean change from baseline HbA1c at endpoint will be produced using the ANCOVA method. Equivalence of Mylan's insulin glargine sequence group to Lantus® sequence group will be established if the 95% confidence interval is within $\pm 0.4\%$ equivalence limits.

The Least Square (LS) means for each treatment sequence group and associated standard errors will be derived. Differences in LS means will be calculated and associated 2-sided 95% confidence intervals will be provided.

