15.2. SECONDARY EFFICACY

The secondary efficacy analyses will be performed for the ITT population.

A repeated measures analysis employing a restricted maximum likelihood (REML)-based, mixed-effects model approach (MMRM) will be used to compare treatment sequence difference at scheduled visits. The MMRM model will include the fixed, categorical effect of treatment sequence group, region, visit, treatment sequence-by-visit interaction and baseline value (52 weeks in MYL-GAI-3001) as covariates. The data collected at Baseline, all schedule visits will be used in the MMRM model for the purpose of analysis. For the drop-out patients, if the last post baseline data is not falling at the scheduled visit, then it will be mapped to the next scheduled visit and this data will also be included in the analysis.

An unstructured covariance matrix will be used to model the within-patient errors. The Kenward-Roger approximation will be used to estimate denominator degrees of freedom. If the model for unstructured covariance matrix fails to converge, the heterogeneous Toeplitz covariance structure, followed by heterogeneous autoregressive covariance structure, will be used. If a structured covariance matrix is used because of the convergence

Document:	\\JEEDC-NAS01A\Biosdata\Mylan\INSULIN_GLARGINE\UXA25824\Biostatistics\Documentation\SAP		
Author:	[name] and [name]	Version Number:	Final V1.0
		Version Date:	[27JUL2016]

Template No: CS_TP_BS016 – Revision 3
Effective Date: 01May2012

Reference: CS_WI_BS005

Copyright © 2012 Quintiles Transnational Corp. All rights reserved.

The contents of this document are confidential and proprietary to Quintiles Transnational Corp. Unauthorized use, disclosure or reproduction is strictly prohibited.

problem, an analysis will be conducted where a sandwich estimator will be used for the fixed effects parameters to take account of possible misspecification of the true covariance matrix.

Above mentioned statistical analysis approach will be performed for all secondary continuous efficacy variables. Contrasts of LS mean at each scheduled visit will be used to evaluate all pairwise treatment sequence group comparisons, and 95% confidence intervals for treatment sequence group differences in LS means will be computed for each visit.

Following efficacy measures (both actual and change values) will be summarized at baseline (week 52 in MYL-GAI-3001) and scheduled visits.

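### A period-3 exit HbA1c stands in for week 36 in the primary analysis, and the planned sensitivity analyses may not test that rule

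*SAP*

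**What the plan says.** - **Schedule.** The Protocol's Schedule of Activities has HbA1c at weeks 0, 12, 24 and 36 only. Visits at weeks 26, 28 and 32 carry no HbA1c.
- **Primary population.** SAP 5.4 requires for mITT a baseline "HbA1c value and one post-baseline HbA1c value at treatment period 3".
- **Primary analysis.** SAP 15.1.3: "The primary efficacy analysis will be performed for the mITT population". SAP 15.1.2: "If week 36 HbA1c is missing then last non-missing values from period 3 will be used". Protocol 9.2.1 has the same rule. SAP 7.3 says nothing is imputed "except when week 36 HbA1c data is missing due to early discontinuation, exit measurement of that period will be used for endpoint".
- **Sensitivity MMRM.** SAP 15.1.4 takes it from the secondary ITT analysis. For a dropout in that analysis, SAP 15.2 says that "if the last post baseline data is not falling at the scheduled visit, then it will be mapped to the next scheduled visit". SAP 6.3 does likewise for tables: "Early termination data will be mapped to the next available visit number for by-visit summaries".
- **Per-protocol check.** SAP 5.5 admits "patients who have at least one baseline and one period 3 value", so an exit value qualifies there too.
- **Multiple imputation.** SAP 7.3 ties it to a condition: "if missing values occur in more than 10% of the patients for HbA1C values". SAP 3.3 and 15.1.4 plan it with no threshold. Neither section says whether a patient with an exit value counts as missing at week 36.
- **Design.** SAP 3: the switching arm spends weeks 12 to 24 on Lantus and returns to the test product at week 24. The other arm stays on Lantus throughout. The SAP regards twelve weeks per period as enough exposure for HbA1c.

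**The concern.** A sample taken soon after week 24 follows twelve weeks in which both arms used Lantus, and less than the twelve weeks of new exposure that the SAP treats as adequate. If the products differ at week 36, such a sample may show only part of the difference. Counting it as week 36 shrinks the estimate, even when exits are random and balanced between arms. In an equivalence trial, shrinkage toward zero helps the claim.

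A sensitivity analysis should expose this. The MMRM appears to place the same value at week 36. If the imputation takes its input from the same mapped data, it sees nothing missing for these patients. The checks could then agree with the primary result because they share its rule, not because the rule is harmless.

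**Working it through.** **1. The plan's own figure.** Inputs from Protocol 9.1 and SAP 3.1: 69 per arm, 10% without a period-3 HbA1c, SD 0.61, limits ±0.4, 95% CI.
- Evaluable: 69 × 0.9 ≈ 62 per arm. SE = 0.61 × √(2/62) = 0.1096.
- Power at no true difference = 2Φ(0.4/0.1096 − 1.96) − 1 = 2Φ(1.691) − 1 = 90.9% (90.4% with the t distribution).
- The stated 90% reproduces.

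**2. Size of the dilution.** Assumed, because the documents give neither: p = share of analysed patients whose endpoint is an exit value, and f = fraction of the week-36 difference that value shows. The lower p of 3.3% is 10%/3: 10% leaving evenly over three periods, with every period-3 leaver sampled. At a true difference of 0.4:
- bias = −p(1 − f) × 0.4
- false equivalence ≈ Φ(|bias|/0.1096 − 1.96), nominal 2.5%

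| p | f | bias | false equivalence |
|---|---|---|---|
| 3.3% | 0.9 | −0.001 | 2.6% |
| 3.3% | 0.5 | −0.007 | 2.9% |
| 3.3% | 0 | −0.013 | 3.3% |
| 5% | 0.9 | −0.002 | 2.6% |
| 5% | 0.5 | −0.010 | 3.1% |
| 5% | 0 | −0.020 | 3.8% |
| 10% | 0.5 | −0.020 | 3.8% |
| 10% | 0 | −0.040 | 5.5% |

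**3. Does the MMRM share it?** Simulation with 20,000 runs, 69 per arm, visit correlation 0.6, true difference 0.4 / 0 / 0.4 at weeks 12 / 24 / 36, random exits, f from 0 to 0.5. With no exit values, the ANCOVA rate on these draws was 2.7%.

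| Analysis | p = 3.3% | p = 5% |
|---|---|---|
| ANCOVA with exit values | 3.1–3.4% | 3.3–4.0% |
| MMRM, exit value at week 36 | 3.0–3.4% | 3.2–3.9% |
| MMRM, week 36 left missing | 2.6% | 2.6% |

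The mapped MMRM behaves like the ANCOVA. The unmapped one does not.

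**4. Power of the unmapped MMRM.** Exit values are dropped on top of the planned 10% loss. No true difference, 8,000 runs, Monte Carlo error about 0.3 to 0.4 points, p as a share of the 69 randomized per arm.

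| Visit correlation (assumed) | p = 3.3% | p = 5% | p = 10% |
|---|---|---|---|
| 0.3 | 89.4% | 88.3% | 86.2% |
| 0.6 | 90.9% | 90.7% | 89.2% |
| 0.8 | 92.4% | 92.3% | 91.4% |

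**5. The imputation trigger.** The planned loss of 10% is 13.8 of 138 patients. If only week-36 values count, which SAP 7.3 does not say, 13/138 = 9.4% means no imputation and 14/138 = 10.1% means imputation. The plan's own expected loss sits on the threshold.

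**6. Values after withdrawal.** Protocol 6.2 keeps some withdrawn patients on the visit schedule. If a random 10% leave and half of them give an off-treatment week-36 value, 5% of patients do so. If the difference is gone by then, bias = −0.05 × 0.4 = −0.020. If half of it remains, bias is −0.010. An unmapped MMRM that counts these values is diluted as well.

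**The case against.** The case for leaving the plan alone has weight.

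- **The effect may be near zero.** The Schedule has no early-discontinuation column. Early-discontinuation or termination visits appear only for pregnancy (Protocol 8.4.1) and trial termination (Protocol 15). Safety withdrawals are followed on schedule and may give a real week-36 sample. Late leavers would show most of the difference. The false-equivalence figures also apply only at a true difference of exactly 0.4. All of this stands, and it is why the point is a modest one.
- **Safeguards exist.** The plan has an ITT MMRM, imputation on visits 5, 9 and 13, and a commitment to investigate conflicting conclusions. These deserve credit, but they test the rule only if exit values are kept out of week 36, which the SAP does not say.
- **The mapping is not explicit.** By visit number, an exit value could land on week 26, 28 or 32. No HbA1c is planned there and the imputation code lists only visits 5, 9 and 13, so week 36 is the natural reading. It remains a reading.

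A reader might infer three stronger claims that the documents do not support.

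- **That an unmapped MMRM must become primary.** It assumes missing at random, sets aside observed values, can fall below 90% power (step 4) and needs Protocol 9.7 changed by amendment under Protocol 12. It is an option for the sponsor.
- **That requiring a period-3 value itself tilts the trial toward equivalence.** Its direction is not fixed. In simulation with leaving tied to the week-12 change, random 10% loss gave no bias. Patients with high values leaving both arms (odds ×5 per 1%) gave −0.020. The same pattern in the Lantus arm only gave +0.034, away from equivalence.
- **That the sample size is wrong.** It is not (step 1).

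**Conclusion.** The concern holds as a gap in the sensitivity analyses, not as a defect that invalidates the primary one. The exit-value rule can only preserve or shrink a difference that builds up after the week-24 switch, and the planned checks may carry the same rule. With exit values in 3.3% to 5% of patients, bias is at most 0.020 against a limit of 0.4 and false equivalence at most about 3.8%. It reaches about 5.5% only if 10% of patients have exit values that show none of the difference. These sizes rest on assumed exit shares and carried fractions, and on exits unrelated to outcome. The change is worth making because it is cheap and would let the equivalence conclusion be checked independently of the rule.

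**What to change.** Keep the mITT ANCOVA as primary.

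1. **SAP 15.1.4:** run the ITT sensitivity MMRM for HbA1c without the forward mapping of SAP 15.2. Treat week 36 as missing unless it was sampled at the week-36 visit, and list exit values at their actual date.
2. **SAP 7.3:** delete the 10% trigger so that the ITT multiple imputation always runs, with exit values set to missing at week 36.
3. **Off-treatment values:** report both week-36 analyses with and without HbA1c taken after withdrawal from treatment.
4. **Tipping point:** shift the imputed switching-arm week-36 values up and down until the 95% CI leaves ±0.4. Illustration at 62 per arm (half-width 1.98 × 0.1096 = 0.217, SE held fixed) with an observed difference of 0.10 and 10% of that arm missing: it tips at (0.4 − 0.10 − 0.217)/0.10 = +0.83 or −(0.4 + 0.10 − 0.217)/0.10 = −2.83. With 20% missing it tips at +0.42 or −1.42.
5. **Decision wording:** call equivalence robust only if the unmapped MMRM and the imputation agree with the primary result.

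Cost: SAP wording, recorded in SAP 3.3 as Protocol 9.2 allows, and a little more analysis. No new patients or data are needed. Sensitivity intervals will be slightly wider: on top of 10% loss, the MMRM's power is about 88% to 92% at 3.3% to 5% exits and 86% to 91% at 10%, for visit correlations of 0.3 to 0.8.
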